Subjects who are not yet adults (infants, children, teenagers)

We are not enrolling participants who are not yet adults.

Cognitively Impaired Adults

We will not enroll cognitively impaired adults.

Adults Unable to Consent

We will not enroll adults who are unable to provide consent.

Documentation of Informed Consent Process

Documentation of the informed consent process is required to establish that the subject was accurately and adequately informed and that no study-related procedures were initiated prior to obtaining informed consent. A research team member will note in the source documentation the consent process, date consent was obtained, and that consent was obtained prior to initiating any research procedures. In the scenario of Remote Informed Consent Process documentation of all actions will be maintained as described in the

Investigator Guidance: Remote Inform Consent Process in Non-Except Research (HRP-831).

Waiver of Written Documentation of Consent or Waiver of Consent

N/A

Randomization

A randomization schedule containing the subject treatment group assignment (EX or CON) will be generated by the study statistician. A permuted blocks approach will be used with subjects stratified by gender. We will use blocks of random sizes of 4 to reach the total sample size of 20 to start (18 completers) in each group.

Study Visits

All study visits will be conducted at the AdventHealth Translational Research Institute.

[figure not shown]

Figure 1: Schematic depiction of the study protocol.

Phase	Description	Duration	Subject at home	Subject Ambulatory	Visit Window
I	Screening	< 35 days	Yes	Yes	35 days within PBR1
II	Pre-Bed Rest	5 days	Yes	Yes	-
III	Bed Rest	10 days	No	No	-
IV	Ambulatory/Exercise Recovery	4 weeks	Yes	Yes	\pm 1 days
V	Optional Resistance Exercise	4 weeks	Yes	Yes	\pm 2 days

Phase I – Screening.

Screening Visit 1

Approximate visit time: ~ 4 hours

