from out bed rest and recovery study in older adults (recovery in leg lean mass over 4 weeks (n=20; mean \pm SD) = $+1.2 \pm 0.5$ kg). Sex will be explored as a biological variable, however, based on data from our previous bed rest and recovery study we do not expect a difference in rate of recovery between men and women (n=10 men $+1.1$ kg, n=10 women $+1.0$ kg lean mass recovery). The sample size will also provide 80% power to detect a significant mean difference of 0.38 AU in muscle mitochondrial OXPHOS protein expression between groups during recovery. The power calculations are based on two-sample t-tests for mean difference with unequal variance and a P-value of 0.05.

Statistical Analysis Plan

The **primary** outcomes, including leg lean mass, protein synthesis rate, and mitochondrial respiration, will be measured at 5 time points following 10 days of bed rest. 2x5 repeated-measures ANOVA will be performed on the dependent variables as a function of intervention (2 levels: EX and CON groups) and time (3 levels: 5x biopsy timepoints). We will also fit mixed models (fixed and random effects) to interrogate the longitudinal data. This will allow us to better account for the longitudinal nature of the data and to explore the influence of other potential predictors of changes in muscle mass. In particular, the relationship between change in IR, protein synthesis and mitochondrial function will be explored. Since many of these outcome variables are from biopsies, e.g., various mitochondria parameters will be correlated with one another, covariance will be explored, and we will also use the relative change measures of these as a bivariate outcome. Sex, race and ethnicity as biological variables will also be explored. Sex will be explored as a biological variable, however, based on data from our previous bed rest and recovery study we do not expect a difference in rate of recovery between men and women (n=10 men $+1.1$ kg, n=10 women $+1.0$ kg leg lean mass recovery).

Potential Risks and Benefits

Potential Benefits

Participants will likely receive no direct benefit from taking part in this research study.

Potential Risks

Blood draws and/or IV (lab samples, e.g.). There is a risk of pain, vasovagal syncope, hematomas, and/or infection at the blood draw site or IV insertion site (low risk of serious AEs).

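### The pilot means for leg lean mass do not agree with each other, and the stated ANOVA leaves out the sex stratum used in randomisation

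*Protocol*

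**What the plan says.** Protocol, Sample Size Determination, supports the 80% power for leg lean mass with an unfilled literature reference and the group's own earlier study: "recovery in leg lean mass over 4 weeks (n=20; mean \pm SD) = $+1.2 \pm 0.5$ kg". It then gives that study by sex: "n=10 men $+1.1$ kg, n=10 women $+1.0$ kg lean mass recovery". The Statistical Analysis Plan section of the protocol repeats the by-sex numbers with a fuller label: "n=10 men $+1.1$ kg, n=10 women $+1.0$ kg leg lean mass recovery". Both sections use them to say "we do not expect a difference in rate of recovery between men and women".

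Protocol, Randomization, states: "A permuted blocks approach will be used with subjects stratified by gender". The Statistical Analysis Plan section sets out the analysis as "2x5 repeated-measures ANOVA will be performed on the dependent variables as a function of intervention (2 levels: EX and CON groups"), with time as the only other factor. Mixed models are also planned, without a fixed list of covariates, and sex is to be explored alongside race and ethnicity. Neither model is labelled primary.

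**The concern.** There are two separate points.

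First, two equal groups with means of 1.1 and 1.0 kg should not pool to 1.2 kg. The pooled mean and its SD are the only leg lean mass inputs shown for the power claim. If the pooled and by-sex figures came from different subsets or measures, a reader cannot tell which people the SD of 0.5 belongs to, and the SD does drive the sample size.

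Second, sex was judged important enough to stratify on, yet it is missing from the only model whose factors are named. If sex predicts recovery, its variance stays in the error term and the precision that stratification could have bought is lost.

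**Working it through.** **Inputs.** Pooled pilot mean 1.2 kg, SD 0.5 kg, n=20; men 1.1 kg (n=10), women 1.0 kg (n=10); 80% power; alpha 0.05 (all Sample Size Determination). Completers: 15 in Sample Size Determination, not stated as per arm; 18 of 20 per group in Randomization. Assumptions: two-sided test; the same SD of 0.5 in both arms, since only one SD is given.

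**1. Pooled mean.** (10 × 1.1 + 10 × 1.0) / 20 = 1.05 kg, against 1.2 kg stated. Rounding to one decimal allows at most (1.15 + 1.05) / 2 = 1.10 kg and at least (1.05 + 0.95) / 2 = 1.00 kg. A mean printed as 1.2 must be at least 1.15 kg. Rounding cannot close the gap.

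**2. Power claim.** It cannot be reproduced, because no EX-CON difference in kg is given. What can be computed is the difference detectable with 80% power at SD 0.5 (noncentral t):

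| Completers per arm | Standardised difference | Difference in kg |
|---|---|---|
| 15 | 1.06 | 0.53 |
| 18 | 0.96 | 0.48 |

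The 15 fits a per-arm reading, since 20 × (1 − 0.25) = 15. The pooled mean does not enter this calculation; only the SD and the number per arm do.

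**3. What the pilot says about sex.** Taking 0.5 as the SD within each sex, the observed difference is 0.1 kg with standard error 0.5 × √(2/10) = 0.224 kg. The 95% interval is 0.1 ± 2.10 × 0.224 = 0.1 ± 0.47, or −0.37 to +0.57 kg.

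**4. Cost of omitting sex in an analysis of recovery (change).** With equal numbers of each sex, a sex difference D adds D²/4 to the variance. Keeping the within-sex SD at 0.5, the inflation of the standard error is √(1 + (D²/4)/0.25) − 1 = √(1 + D²) − 1, with D in kg:

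- D = 0.1: √1.01 − 1 = 0.5%
- D = 0.3 (illustrative): √1.09 − 1 = 4%
- D = 0.57 (upper limit from step 3): √1.325 − 1 = 15%

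**5. Which term helps.** In the repeated-measures model, recovery is tested by the group-by-time term against within-person error. A sex main effect is constant over time within a person and cancels from within-person change, so adding it alone leaves that error as it was. It sharpens only the group main effect on the level of leg lean mass. The sex-by-time term is what removes a sex difference in recovery from the group-by-time error. In an analysis of change, sex as a single covariate does the same job.

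**The case against.** The strongest reply on the figures is that they may not describe the same thing. Sample Size Determination labels the by-sex numbers as lean mass without the word leg, and the by-sex means are cited only for the sex expectation, not for power. They could be the wrong ones, with 1.2 ± 0.5 kg intact. That stands as far as it goes: the documents do not identify the culprit. But 10 + 10 = 20, both sets are ascribed to the group's own bed rest and recovery study, and the analysis section does say leg lean mass. If another measure was meant, that label is wrong instead.

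A reader might go further and infer that the pilot mean is overstated by 1.2 − 1.05 = 0.15 kg and that the trial is therefore undersized. The protocol does not support this. It would mean choosing which figure is wrong, and a single-cohort mean does not set the sample size.

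On the model, covariates are often left to a separate analysis plan, and the mixed models may take up sex. That is fair, but the protocol itself names the ANOVA factors, and a promise to explore sex is not a commitment to analyse by the stratum. A reader might also infer that omitting it invalidates the test. It does not: the standard error is somewhat too wide, which is conservative.

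Nor should the cost be put at 22% for a 0.57 kg difference. That result treats 0.5 as the total SD, while the 0.57 limit treats 0.5 as the within-sex SD. With a total SD of 0.5 the within-sex SD would be √(0.25 − 0.081) = 0.41, and the upper limit about 0.49 kg.

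Finally, the interval in step 3 shows that the pilot cannot rule out a sex difference. It is tempting to ask that the expectation of no difference be struck out. But it is worded as an expectation, and the protocol still stratifies by gender, recruits men and women in about equal numbers and explores sex. Removing the sentence would change nothing the trial does.

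**Conclusion.** The pilot figures contradict each other if they describe the same 20 people and the same outcome, which is the natural reading of the text. The by-sex means imply 1.05 kg (1.00 to 1.10 kg with rounding), not 1.2 kg. Which figure is wrong is unknown. No effect on sample size or power can be computed, because the EX-CON difference behind the 80% claim is not stated.

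Analysing by the randomisation stratum is a real but modest improvement. Its value depends on the true sex difference in recovery: negligible at the pilot's own 0.1 kg, and a standard error about 4% to 15% smaller than the inflated one would suggest is at stake only at 0.3 to 0.57 kg, given a within-sex SD of 0.5 and equal numbers of men and women. Both points deserve correction; neither threatens the validity of the trial.

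**What to change.** 1. Recompute the overall mean, the two sex means and the SD from the pilot data. Correct the text in both sections and use one label for the outcome.
2. State the EX-CON difference in kg on which the 80% power rests, and whether the completers are counted per arm. If SD 0.5 stands, this is about 0.53 kg with 15 per arm or 0.48 kg with 18 per arm.
3. Name the primary repeated-measures model and include sex and sex-by-time as fixed terms, or use sex as a covariate in an analysis of change.

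The cost is a recalculation and a few error degrees of freedom: with two sexes and five time points, (2 − 1) = 1 for sex and (2 − 1) × (5 − 1) = 4 for sex-by-time. No new data are needed.

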After study aims have been achieved and study related endpoints have been measured and analyzed, any remaining biospecimens will be stored at the TRI Laboratory Room 2404 and will then be considered as "archived biospecimens." Archived biospecimens will be used for any additional hypothesis-related experimentation or testing for the **purposes of**

this study, consistent with the original aims, which cannot be predicted at the time the protocol is developed due to the evolving nature of scientific exploration.

Additionally, archived biospecimen samples may be stored indefinitely for future research. Archived biospecimens could be used for **separate research** by **both** AdventHealth Orlando scientists and scientists outside of AdventHealth Orlando. This would be allowed for **research of any type** (without limitation to disease, process, or research methods) if it has scientific merit as determined by the Principal Investigator, with an additional review by the respective Program Director. For research outside of AdventHealth Orlando, a Material Transfer Agreement will be obtained, which will govern the transfer and chain of custody of the biospecimens outside of AdventHealth Orlando.

Study Outcome Measures (Endpoints)

The primary outcomes, including leg lean mass, protein synthesis rate, and mitochondrial respiration, will be measured at 5 time points (immediately following bed rest, and on weeks 1, 2, 3, and 4 of Recovery Phase).

Data Management and Quality Plan

Data De-identification

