The duration of study data retention will be determined by governing FDA regulations and/or sponsor contract mandate (if applicable). TRI retention policy is maintained in the Records Management Policy. Electronic de-identified data will be kept indefinitely in our database.

Data Quality

Data quality control will occur according to our SOPs on Data Entry, Quality Control Procedures and Query Management. All data will be entered into an electronic data capture (EDC) system and checked against the paper source for accuracy by a second party (Data Entry SOP) and errors resolved through the Query Management SOP. Ten percent of the data points will be routinely checked at the beginning, middle, and close of a study for quality control (Quality Control SOP). Finally, all critical endpoints (as determined by the PI or Sub-I) will be assessed using quality control analyses. The data will be exported into the study database.

The device data will directly be imported into spreadsheets or entered and confirmed into the EDC. Data from the VO2max, activity monitors, and DEXA data are exported directly into spreadsheets for further calculations. Data for each of the endpoint analyses will be imported into an SAS database linked with a participant ID.

Data Sharing (outside of AdventHealth Orlando)

This is a collaboration partnership between TRI, the Sponsor, and its affiliates. Certain data elements will need to be shared along with the biospecimen samples (primarily satellite cell cultures). Should archived biospecimens be needed for research outside of AdventHealth Orlando and certain data elements that are connected to the archived biospecimen samples be needed to conduct the research, then Data Use Agreement(s) will be obtained. The Data Use Agreement(s) will identify the purpose for data sharing, the specific data elements to be shared, and will govern the sharing of data related to this study. Data will be de-identified, but a link/code is managed within an electronic research management system and maintained by a study coordinator.

Sample Size Determination

Fifteen (15) participants are expected to complete the study after conservatively estimating a 25% drop-out rate. This will be sufficient to provide 80% power to detect a significant mean difference in leg lean mass between groups during recovery, based on previously published data (REF), and

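### The protocol lists a 2x5 repeated-measures ANOVA ahead of the mixed model for the primary outcomes without saying which leads; the mixed model should be named, because the classical ANOVA handles drop-out and serial correlation less well

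*Protocol*

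**What the plan says.** The primary outcomes are leg lean mass, protein synthesis rate and mitochondrial respiration. Under Study Outcome Measures (Endpoints) they "will be measured at 5 time points (immediately following bed rest, and on weeks 1, 2, 3, and 4 of Recovery Phase").

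The Statistical Analysis Plan section of the protocol goes straight from these outcomes to the statement that a "2x5 repeated-measures ANOVA will be performed on the dependent variables as a function of intervention (2 levels: EX and CON groups) and time". It continues: "We will also fit mixed models (fixed and random effects) to interrogate the longitudinal data". The reason given is "This will allow us to better account for the longitudinal nature of the data", together with exploring predictors of change in muscle mass. The word primary describes the outcomes; neither analysis is ranked.

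Drop-out is stated in two ways. Sample Size Determination says "Fifteen (15) participants are expected to complete the study after conservatively estimating a 25% drop-out rate". Randomization gives a "total sample size of 20 to start (18 completers) in each group".

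Under Data Collection and Follow-up for Withdrawn Subjects, data from withdrawn participants are kept and may enter later analyses.

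**The concern.** The analysis placed first fits this design less well than the one placed second, for two reasons.

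- **Incomplete records.** The classical 2x5 ANOVA needs all five values. A participant who leaves after week 2, or whose tissue fails one assay at one biopsy, contributes nothing to that outcome. This sits poorly with the expected drop-out and with the provision for analysing withdrawn participants' data. Only the EX arm attends supervised training three days a week for four weeks, so loss could differ by arm. If that loss is also related to outcome, the EX-CON difference among completers is biased.
- **Sphericity.** The within-participant F tests, including group-by-time, assume sphericity. Weekly serial measurements often depart from it, because adjacent weeks are more alike than distant ones.

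With neither analysis named as leading, it is also open which result will be reported as the answer if the two disagree.

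**Working it through.** **1. The protocol's own counts.** Inputs: 20 starters per arm (Randomization) and 25% drop-out with 15 completers (Sample Size Determination, which does not say per group).

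- 20 x (1 - 0.25) = 15, so the 15 is reproduced if read as per arm.
- 18/20 = 0.90, so Randomization implies 10% drop-out.
- A complete-record ANOVA would therefore exclude 20 - 15 = 5 per arm (10 of 40) or 20 - 18 = 2 per arm (4 of 40), before any single missed visit or failed assay.

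**2. What the mixed model could recover.** It uses any participant with at least one post-bed-rest value. Participants lost before that add nothing to either method. The protocol does not split drop-out by phase, so the recoverable number is 0 to 5 per arm at 25%, or 0 to 2 at 10%.

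**3. Scale of effect.** No target difference in leg lean mass is stated. With the stated SD of 0.5 kg, 15 per arm and alpha 0.05 (two-sided assumed), the noncentral t distribution gives 80% power at 0.53 kg. A true difference of 0.50 kg is used below.

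**4. Bias of the completer estimate (illustration).** Assumptions: 400,000 simulated participants per arm; mean week-4 gain 1.5 kg (EX) and 1.0 kg (CON); SD of individual gain 0.45 kg and measurement SD 0.15 kg. The SD of observed change is then sqrt(0.45² + 2 x 0.15²) = 0.50 kg, which matches the protocol. Drop-out occurs after weeks 1 to 3. Where it is outcome-related, smaller observed gains make leaving more likely (log-odds 1 per SD).

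| Drop-out pattern (EX / CON) | Completers, kg | Likelihood, kg |
|---|---|---|
| 25% random / 25% random | 0.50 | 0.50 |
| 25% outcome-related / 25% outcome-related, same mechanism | 0.50 | 0.50 |
| 25% outcome-related / 25% random | 0.59 | 0.50 |
| 40% outcome-related / 10% outcome-related | 0.60 | 0.50 |
| 25% random / 25% outcome-related | 0.42 | 0.50 |

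The bias runs from 0.42 - 0.50 = -0.08 kg to 0.60 - 0.50 = +0.10 kg. It is nil when loss is random or acts alike in both arms. The likelihood estimate stays at 0.50 because drop-out here depends only on observed values.

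**5. Type I error of the group-by-time test.** With k = 5 visits and N = 30 participants, F = [SS(interaction)/(k - 1)] / [SS(error)/((k - 1)(N - 2))], on 4 and 4 x 28 = 112 degrees of freedom. Greenhouse-Geisser multiplies both by epsilon = tr(M)² / [(k - 1) tr(M²)], where M is the centred covariance matrix. There were 40,000 null trials per pattern; the Monte Carlo standard error near 5% is sqrt(0.05 x 0.95/40,000) = 0.001.

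| Covariance pattern (assumed) | Epsilon | Uncorrected | Greenhouse-Geisser |
|---|---|---|---|
| Compound symmetry | 1.00 | 0.050 | 0.041 |
| AR(1), 0.5 | 0.81 | 0.064 | 0.046 |
| AR(1), 0.7 | 0.69 | 0.075 | 0.049 |
| AR(1), 0.9 | 0.58 | 0.079 | 0.046 |
| Random slope, moderate | 0.63 | 0.074 | 0.046 |
| Random slope, strong | 0.35 | 0.109 | 0.051 |

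The between-arm main effect compares participants' averages over visits and does not depend on sphericity.

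**The case against.** The strongest reply is that the protocol commits to less than the criticism supposes.

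- **Ranking.** A reader might infer from sentence order that the ANOVA is the confirmatory analysis. The text does not say so, and it credits the mixed model with handling the longitudinal structure better. This stands: the gap is that no lead analysis is named.
- **Complete cases and no correction.** Neither is in the text. Both are properties of the classical method, and the provision on withdrawn participants points the other way. Missing-data rules and sphericity corrections are commonly left to a separate analysis plan, which is not at hand, so their absence is not the finding. What remains is that the protocol itself names a particular method that fits its design less well than another it also names.
- **Drop-out.** Taking 25% as the planned figure ignores the 18 of 20 completers under Randomization. Both must be carried.
- **Power.** It is tempting to go further. If 5% or 10% of values are also lost per visit, 15 x 0.95^5 = 11.6 or 15 x 0.90^5 = 8.9 per arm are complete, and t-test power falls from 80% to about 68% or 55%. The documents do not support reading this as the cost of the ANOVA. The per-visit loss is assumed and stacked on 25% drop-out, the test is not the group-by-time F, and the comparison is with no missing data, not with the mixed model.
- **Bias and error rate.** A reader might infer that both are certain. They are not: the bias needs outcome-related loss that differs by arm, for which the protocol gives no evidence, and the inflation needs non-sphericity and an uncorrected test.

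**Conclusion.** The point holds as a modest, specific improvement. Two analyses of the same primary outcomes are listed, neither is named as leading, and the one listed first is the weaker for five serial measurements with 10% to 25% expected drop-out.

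Run in its classical form, the ANOVA would exclude 2 to 5 of 20 participants per arm. Its completer estimate could be off by about 0.1 kg in either direction on a true 0.5 kg, but only if outcome-related loss differs between arms. Its uncorrected group-by-time test would reject in about 6-8% of null trials under AR(1) correlation of 0.5 to 0.9 at 15 per arm, and more under a strong random slope. The rate is 5% under compound symmetry and 4-5% with Greenhouse-Geisser.

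These figures rest on assumed covariance and loss patterns; they show what can happen, not what will. The mixed model's advantage on bias assumes that loss depends on observed values, and it cannot recover participants lost before the first post-bed-rest value.

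**What to change.** In the Statistical Analysis Plan section, name the planned mixed model as the primary analysis of the primary outcomes:

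- arm, visit and arm-by-visit as fixed effects;
- all randomised participants with at least one post-bed-rest value;
- likelihood-based estimation with small-sample degrees of freedom.

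Drop the 2x5 ANOVA, or keep it only as a sensitivity analysis with a Greenhouse-Geisser correction.

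In the same edit, correct the time factor, described as "time (3 levels: 5x biopsy timepoints") although there are five visits, and reconcile the 15 completers in Sample Size Determination with the 18 in Randomization.

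The cost is wording only: no new participants, visits or assays, and the mixed model is already planned. Any separate analysis plan should be aligned.
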